### **Ethical considerations**

Ethical approval for the overall research project will be obtained from the University of Manitoba and will be sought at each individual study site, including the University of Calgary, Health Research Ethics Board for the Calgary site. There are no specific risks associated with participation in this research project. While there will be time commitments associated with attending the focus groups, patient and caregiver participants will be provided with \$50 for their time and expenses. The time required for participating in the priority-setting process workshop will be two full days, including one overnight, of which participants will incur no costs; all travel, accommodation, food and per diems will be provided. In addition, participants will contribute their voices and opinions to the improvement of clinical service provision.

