**Study Setting:**

Two 12-week DBT sessions (one virtual and one in-person) will be provided. The in-person sessions will be held weekly at the Seven Oaks General Hospital Campus in meeting rooms away from the hemodialysis unit. Virtual sessions will be video conferences held using the MS Teams platform.

**Study Population:***Inclusion Criteria:*

- Age  $\geq$  18 years old
- Individuals followed in the Manitoba Kidney Health Program at the SOGH or HSC sites with advanced chronic kidney disease not yet on facility-based hemodialysis but with plans to start within 1 month; OR
- Individuals followed in the Manitoba Kidney Health Program at the SOGH or HSC sites who have initiated facility-based hemodialysis within the last 90 days
- Able and willing to attend weekly DBT sessions (either virtually or in-person)
- Experiencing self-reported psychological distress related to advanced kidney disease or initiation of hemodialysis
- Deemed eligible to participate by study clinical psychologist

*Exclusion Criteria:*

- Unable to complete intervention due to planned relocation/transplant/modality change
- Unable to communicate in English
- Deemed by hemodialysis unit staff/physician/study psychologist to be unable to participate fully in study activities due to:
  - Actively participating in psychiatric care with psychiatric (DSM-5) diagnosis
  - Requiring referral for psychiatric care as per facility-based HD care provider assessment
  - Current psychotic symptoms
  - Cognitive impairment that would limit ability to participate in group or complete homework
  - Safety risk to staff (e.g. physical aggression)
  - Antisocial personality disorder or other issues that may limit ability to constructively participate in peer group
  - Severe comorbid substance use disorder (if present will offer referral to addictions resources or Addictions Psychiatry)

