**Table 1: Proposed Weekly Schedule for 12 Week DBT Program Delivery**

Weeks 1-3: Mindfulness (Foundation for All Skills)	
Week 1: Introduction to DBT & Core Mindfulness	Overview of DBT and group expectations
	What is mindfulness? (Wise Mind, Reasonable Mind, Emotion Mind)
	Exercise: "Leaves on a Stream" meditation
	Homework: Mindfulness practice (observe and describe one activity mindfully)
Week 2: Mindfulness – What & How Skills	What Skills: Observe, Describe, Participate
	How Skills: Non-judgmentally, One-mindfully, Effectively
	Exercise: "Five Senses Grounding"
	Homework: Practice a "What" skill daily
Week 3: Practicing Mindfulness in Daily Life	Barriers to mindfulness
	Self-compassion and present-moment awareness
	Exercise: Body scan meditation
	Homework: Daily mindfulness journaling
Weeks 4-6: Distress Tolerance (Coping with Crisis Without Making It Worse)	
	Distraction skills (ACCEPTS: Activities, Contributing, Comparisons, etc.)

Week 4: Crisis Survival Skills – ACCEPTS & TIPP	TIPP (Temperature, Intense Exercise, Paced Breathing, Paired Muscle Relaxation)
	Exercise: Cold water face immersion (TIPP)
	Homework: Try two ACCEPTS skills during distress
Week 5: Reality Acceptance – Radical Acceptance & Willingness	What is radical acceptance? Letting go of suffering
	Turning the mind toward willingness
	Exercise: Half-smile & Willing Hands
	Homework: Notice resistance and practice radical acceptance
Week 6: Self-Soothing & Improving the Moment	Mindfulness of current thoughts
	Self-soothe with the five senses
	IMPROVE skills (Imagery, Meaning, Prayer, Relaxation, etc.)
	Exercise: Create a self-soothe kit
	Homework: Practice self-soothing at least twice this week
Weeks 7-9: Emotion Regulation (Understanding & Managing Emotions)	
Week 7: Understanding Emotions & Checking the Facts	Why we have emotions & how they work
	Checking the facts to reduce emotional intensity
	Exercise: Identify an emotion and fact check it
	Homework: Use "Check the Facts" worksheet on a distressing emotion
Week 8: Opposite Action & Problem-Solving	Opposite action: Changing emotions by acting opposite
	When to problem-solve vs. when to accept
	Exercise: Role-play opposite action for anger
	Homework: Use opposite action in a real-life situation
Week 9: Building a Life Worth Living – ABC PLEASE	Mindfulness Review
	Accumulate positive experiences

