### **Risks and Benefits of Study Participation:**

Participants in this study will discuss and be asked about their mental health. Previous work has demonstrated that asking adult research participants about their past experiences in these domains is no more distressing than asking about other personal experiences (e.g. scholastic achievement; body image) and is not typically harmful.

It is possible that some participants will find participating in the survey, PSP, DBT pilots and focus groups therapeutic and/or rewarding. Participants may benefit from improving mental health and building connections with other patients going through similar experiences. Some people may find it meaningful to be part of a research project. The information we learn from the project will benefit society's understanding of the challenges to mental health in people receiving hemodialysis and their solutions.

However, no benefits related to study participation can be guaranteed. DBT participants will be reimbursed for their transportation to in-person DBT group sessions and will share a meal or snack with other group participants. Focus group participants will receive a \$50 honorarium for their time and expenses related to attendance. Additional reimbursement for childcare as needed will be provided as well.

Conversely, it is possible that some participants may experience psychological discomfort while participating in DBT or focus group sessions and/or while answering questions related to study activities. To minimize the possible distress due to answering questions about mental illness, participants will be told during the consent process that they may skip any questions that make them feel uncomfortable and that they are free to discontinue participation at any time without penalty.

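### The ethics section's blanket no-risk statement conflicts with the protocol's own risk and confidentiality sections, and the physical content of DBT Week 4 appears in no risk text and no written eligibility criterion

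*Protocol*

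**What the plan says.** **Risk statements.** Ethical considerations: "There are no specific risks associated with participation in this research project". Risks and Benefits of Study Participation: "it is possible that some participants may experience psychological discomfort while participating in DBT or focus group sessions". The section on anonymity and confidentiality adds that neither can be guaranteed for the workshop, the DBT pilot or the focus groups, because these take place in groups.

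**Curriculum.** The table is headed "Table 1: Proposed Weekly Schedule for 12 Week DBT Program Delivery" and is not restricted to one of the two groups. Week 4 teaches "TIPP (Temperature, Intense Exercise, Paced Breathing, Paired Muscle Relaxation") and lists as its session activity "Exercise: Cold water face immersion (TIPP").

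**Population.** Eligible people are those "who have initiated facility-based hemodialysis within the last 90 days" or those "with advanced chronic kidney disease not yet on facility-based hemodialysis but with plans to start within 1 month".

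**Eligibility.** The exclusion that involves clinical staff reads "Deemed by hemodialysis unit staff/physician/study psychologist to be unable to participate fully in study activities due to", followed by a list of specific reasons. A separate inclusion item requires the study clinical psychologist to judge the person eligible, without stating on what grounds.

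**The concern.** The risk statement is the protocol's summary of what participants are exposed to. An unqualified denial of specific risk that the same document contradicts is wrong as it stands, whatever view one takes of Week 4.

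Week 4 then adds a different kind of content. The rest of the risk text and its safeguards are built around a talking intervention: participants may skip questions or withdraw, they receive mental-health resources, and routine kidney care looks after their well-being because of the mental-health topic. A physical activity in people close to the start of hemodialysis falls outside that frame, and no written step asks anyone who knows the person's medical condition to consider it. At stake are the accuracy of the risk statement and whether screening is done with the actual programme content in view.

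**Working it through.** No arithmetic formula applies, and the plan gives no figure to reproduce. The check sets the sections side by side.

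**1. Is the no-risk sentence consistent with the rest of the protocol?**

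| Section | Position on risk |
|---|---|
| Ethical considerations | No specific risks, for the project as a whole |
| Risks and Benefits of Study Participation | Psychological discomfort possible in DBT and focus groups |
| Anonymity, Confidentiality and Data Security | Confidentiality in groups cannot be guaranteed |

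The first row contradicts the other two, so the sentence fails before Table 1 is considered. The rest of the Ethical considerations paragraph deals with focus groups and the workshop and does not mention DBT. It may not have been written with the DBT pilot in view, but that is an inference.

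**2. Is Week 4's physical content covered by any risk text?** Week 4 has two physical elements. Cold-water face immersion is the listed session exercise. Intense exercise is one named part of the TIPP skill; it is taught, and it is neither the session exercise nor the homework, which draws on the ACCEPTS skills. Neither element appears in the risk section or in Ethical considerations.

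**3. Is it covered by any written eligibility step?**

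- *Inclusion criteria:* age, kidney-care status, ability and willingness to attend, self-reported distress and the psychologist's judgement. None bears on a physical exercise.
- *Exclusion for inability to participate fully:* seven listed reasons, covering psychiatric care or referral, psychotic symptoms, cognition, safety risk to staff, personality or group-behaviour problems, and substance use. None concerns the person's physical health. The words that introduce the list tie the exclusion to those reasons.
- *Other exclusions:* planned relocation, transplant or modality change, and not being able to communicate in English.
- *Psychologist's judgement:* open-ended, with no stated physical criterion.
- *Circle-of-care screen:* the recruitment section bases it on the inclusion criteria. Table 2 lists both inclusion and exclusion at Visit 0. On either reading, the criteria contain nothing on this point.
- *Medical data:* Table 2 places final eligibility at Visit 0 and medical history at Visit 1. The data-collection section says comorbidities are collected at the time of consent, which Table 2 places at Visit 0. Whichever timing applies, nothing links these data to eligibility or to Week 4.

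**4. How many people could it reach?** Planned recruitment in Manitoba is 15 in-person plus 20 virtual: 15 + 20 = 35. This is a ceiling for Manitoba, since not everyone will attend Week 4 and the in-person target already allows for no-shows and dropouts. The focus-group section says the same protocol, including the DBT study, will run in Halifax, but gives no DBT sample size there.

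**The case against.** The strongest reply is that no passage says face immersion or learning about intense exercise is risky in this population. A curriculum item is not a risk statement, so Table 1 cannot contradict the ethics text, and only a small wording conflict with the risk section remains. The first part of this is right: the documents give no size for any physical risk, and this point does not supply one. What survives is that the protocol schedules physical content on which its risk, ethics and eligibility text is silent, alongside an absolute statement that is already false on other grounds.

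Four stronger readings are tempting, and the documents do not support them:

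- *Participants are not told.* Consent pages were not available, and the protocol provides for a written consent form reviewed with the coordinator and at least 24 hours to decide. The silence is shown only for the protocol's own sections.
- *The treating team is bypassed.* Unit and clinic staff receive a letter and a presentation, a circle-of-care member screens, and staff or a physician can invoke the exclusion. What is missing is a written criterion, not their involvement.
- *Virtual participants are unsupervised.* The psychologist and a co-facilitator with a healthcare degree attend by video. They are not physically present, but they are not absent.
- *The exercise is fixed for everyone.* Table 1 is a proposed schedule, and the virtual programme may be modified after the in-person group. It is, however, the only curriculum given, and the in-person group runs first.

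Participants also meet the psychologist at an orientation beforehand and may stop at any time. These provisions help, but they do not put the Week 4 content in front of whoever judges eligibility.

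**Conclusion.** The point holds in two parts. First, the no-risk sentence is contradicted by two other sections of the same protocol; this rests on the text alone. Second, the Week 4 physical content is absent from the protocol's risk and ethics sections and from every written eligibility criterion. The second part assumes that Table 1 is delivered broadly as proposed, and it is limited to the protocol, since the consent form may say more.

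The reach is at most 35 planned participants in Manitoba, up to 20 of them attending remotely, plus an unstated number in Halifax. No probability or severity of physical harm can be derived from the documents, and none is claimed. The feasibility outcomes and their analysis are not affected. The change is more than editorial, because it concerns the accuracy of the risk statement and what the eligibility screen considers, but it is a modest correction.

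**What to change.** 1. Remove or correct the no-risk sentence in Ethical considerations so that it agrees with the risk section and the confidentiality section.
2. In the risk section, name the Week 4 physical components of Table 1 alongside psychological discomfort, and check that the consent form says the same.
3. Have the inclusion/exclusion screen that the circle of care already performs at Visit 0 take those components into account.

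How the components are handled clinically, including whether and in what form they stay in the in-person and virtual programmes, is for the sponsor's clinicians to decide and state; no rule is proposed here.

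The cost is a slightly less favourable risk statement and one added item in an existing screen. No extra visit is needed.

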### **Data management**

We will maintain appropriate research records for this study, in compliance with ICH-GCP, and institutional requirements. For this study, CRFs will be the primary record of the patients' participation in the study but will be supplemented by hard copy/electronic documentation of outcome assessments (e.g. completed surveys and questionnaires).

Data will be submitted for every survey respondent and DBT pilot or focus group participant who is enrolled in the study, regardless of duration via transcription of paper Case Report Forms or direct entry into RedCAP, a secure electronic data capture system housed at the University of Manitoba. Data available from the source documents will be de-identified using a dedicated participant ID number. No identifiable information will be entered.

Paper CRFs will be completed in black or blue ink only and be legible. If an entry on a CRF requires change, the correction will be made by drawing a single line through the incorrect entry, followed by entering the correct data and initialing and dating the entry. Correction fluids, markers, erasures or any form of obliteration on the CRFs will not be permitted. All fields will be completed. If data are not available, a straight line will be drawn through the applicable fields and the words "None" or "N/A" will be written. The study research assistant will be responsible for entering the data into the secure, password-protected computerized REDCap database.

### **Anonymity, Confidentiality and Data Security**

All members of the research team will respect study participants' privacy and confidentiality throughout the study. Measures will be taken to ensure that all the data collected for this study will remain confidential in accordance with privacy legislation. Study personnel will not transmit documents, other than that previously specified, or samples containing personal health identifiers (PHI) at any time over the course of the study. Each participant will be assigned a unique code and these numbers rather than names will be used to collect, store, and report participant information. Full names and other identifying information will not be revealed unless required by law and/or for the applicable REB review, or for auditing purposes. The Subject Identification Code List (i.e. participant key) that links the identity of the participant with subject ID for de-identified data will be maintained with the trial master file. The master file will be maintained both in electronic and hard copy format. The electronic file will be encrypted and stored on a dedicated research server that only the PI and study research staff will have access to. The identity of the participants will not be revealed in any published data or in presentation of the information obtained as a result of this study. Findings will be reported in aggregate.

Anonymity and confidentiality will be maintained as much as possible for PSP, DBT pilot intervention and focus group participants but cannot be guaranteed due to the nature of group participation. Ground rules will be established and reviewed at the beginning and end of the PSP workshop, each DBT session and focus group emphasizing the confidentiality of information shared within the group. Taking these precautions will assist in maintaining confidentiality of the data collected. Audio recordings and questionnaires will be stored in a locked filing cabinet in a locked office at the University of Manitoba for a period of 10 years after study completion and will then be destroyed. Electronic data including the study participant key and transcripts of audio files will be

kept in REDCap or a password-protected file on a research server at University of Manitoba accessible only to [name] and research staff involved in the study for 10 years. Anonymous quotes from the focus groups, interviews, surveys, DBT groups, and PSP may be presented in the publications of aggregate results for illustrative purposes.

Study records will be retained for 10 years after study completion. When the archiving requirements have expired, any written records associated with this study will be destroyed using confidential shredding and the electronic database used for analysis will be deleted.

**Appendix A. Project Framework Updated 2025**

Column A: Grant Year	Column B: Objectives	Column C: High-Level Key Activities
Years 1-2	
Key Objective 1: Develop an accessible inventory of all mental health supports available to Canadians on hemodialysis.
 
Knowledge to Action Framework Stage:
 
- Identify problem, review, select knowledge
	
	
Sub-Objective 1.1
 
Perform an environmental scan of mental health resources for people receiving dialysis treatment across Canada
	
A. Identify resources in each province - Complete
 
 
• One province at a time, conduct Google/web search for resources, including health agencies and public facing
 
• Maintain an audit trail of environmental scan
 
• Identify target audience (i.e. patients and clinicians) and tailor accordingly
 
• Identify kidney specific / generic mental health and organize accordingly
 
• Identify French-speaking collaborators to help with Quebec resources
 
• Consult kidney experts, including multidisciplinary practitioners, KFOC, and patient partners to solicit feedback
 
 
(Led by [name])

		
B. Identify and connect with consultants in each province to confirm resources - Complete
 
 
• Consult experts, including patient partners, on the environmental scan for each province
 
• Identify gaps in resources to be addressed in subsequent phases of project (Led by [name]/[name]/Provincial Leads)
 
 
C. Identify resources for mental health care specifically Indigenous people in Manitoba - Complete
 
 
• Consult with Indigenous organizations in Manitoba (FNHSSM and Ongomiizwin)
 
• Consult with Indigenous patient partners and healthcare providers
 
• Consult with Indigenous Knowledge Keepers (project Knowledge Keeper) (Led by [name])
 
 
D. Consult and partner with other mental health associations in Canada to ensure resources are identified in environment
 
 
• Canadian Mental Health Association
 
• Mental Health SPOR Network (Led by [name]/[name])
 
 
E. Develop content to make environmental scans accessible online - Complete
 
 
• As each province's environmental scan is completed, work with Can-SOLVE web designer ([name]) and health agencies to finalize and house the final resource (Led by [name])
 

--	--	--

Years 1-2	Key Objective 2: Identify culturally sensitive, individualized approaches to mental health care for people on hemodialysis	
	Knowledge to Action Framework Stage: -Adapt knowledge to local context/Assess barriers/Select and Tailor Interventions	
	
Sub-Objective 2.1
 
Identify key targets, components, priorities, and preferences for individualized mental health support strategies for Canadians on hemodialysis
	
Survey / Prioritizing Exercise using James Lind Alliance approach Complete
 
 
• Which aspects of mental health in hemodialysis are most important to address?
 
• What treatments are most acceptable and have potential to help? Complete
 
• Where/how/by who should mental health care be provided? (e.g. in HD unit, online, group, individual, family)
 
• Discuss with different stakeholders how to adapt these aspects into intervention Ongoing
 
• Discuss specific aspects of mental care with Indigenous representatives' (see Obj 2.2 below)
 
 
(Led by [name]) Ongoing

	
Sub-Objective 2.2:
 
Identify challenges to mental health care for Indigenous people on hemodialysis
	
Qualitative study identifying challenges to care in Indigenous individuals receiving hemodialysis in Manitoba – Engage groups ongoing
 
 
• Engage Indigenous community in Manitoba (FNHSSM/Ongomiizwin) for feedback, comments and consensus
 
• Present findings to community and clinicians with recommendations for support Pending
 

	
Sub-Objective 2.3
 
Identify the effect of gender on key challenges and lived experiences in individuals with depression receiving hemodialysis
	
A. Nursing knowledge in hemodialysis and depression care –
 
 
• Integrative review, guided by Whittemore and Knafl
 
 
B. Synthesis on sex and gender differences in people receiving dialysis and experiencing depression
 
 
• Scoping review, guided by Arksey and O'Malley, updated by Levac
 
 
C. Qualitative study, guided by Interpretive Description, exploring adult women's experiences of depression while receiving dialysis
 
 
• Present findings to clinicians, along with recommendations for support
 
 
(Led by PhD trainee, [name]; [name])

Years 3-4	
Key Objective 3: Informed by Objectives 1 and 2, develop, implement and evaluate optimal evidence-based mental health support strategies for Canadian
 
Knowledge to Action Framework Stages:
 
-Adapt knowledge to local context/Assess barriers/Select and Tailor Interventions
 
- Implement Interventions, Monitor Knowledge Use, Evaluate Outcomes
 
Implementation Framework: Consolidated Framework for Implementation Research (CFIR)
 
Evaluation Framework: Reach, Effectiveness, Adoption, Implementation, Maintenance Framework (RE-AIM)
	
	
Sub-objective 3.1
 
Develop an intervention to support mental health care for individuals receiving hemodialysis in Manitoba (and Nova Scotia – currently)
	
Using an iterative approach and engaging community stakeholders/patient partners/clinicians - Ongoing
 
 
• Incorporate information obtained from Objectives 1 and 2
 
• Develop intervention addressing a priority mental health issue Identified in Obj 2.1 and 2.2 
 
◦ Submit ethics for Dialectical Behavioural Therapy (DBT) Pilot Intervention
 
◦ Recruitment
 
 
 
• Develop implementation strategy for this intervention 
 
◦ Implement & evaluate DBT Pilot Intervention
 
◦ Focus Groups to tailor DBT Pilot Intervention
 
◦ Analysis and further tailoring of DBT Pilot Intervention
 
◦ Additional tailoring of DBT Pilot Intervention for Indigenous people on HD
 
◦ Knowledge Translation
 
 
 
• Develop evaluation plan for this implementation strategy
 
 
(Led by [name])

	
Sub-Objective 3.2
 
Implement and evaluate pathway for mental health care for Albertans receiving dialysis
	
Using a person-centred evaluative framework - Ongoing
 
 
• Develop knowledge translation strategies to support implementation of the pathway
 
• Evaluate pathway using person-centred outcomes (patient-reported outcome measures) and person-centred quality
 
 
(Led by [name])

	
Sub-Objective 3.3
 
Provide recommendations on how to tailor a Mental Health Pathway for other Canadian provinces
	
Tailor Alberta's pathway for mental health (e.g. assessment tools; dedicated staff member) A) MB context, and B) NS
 
yet
 
(Led by [name]/[name]/[name])

